## TRILUMINATE Pivotal CIP (Version F)

subjects had been treated outside of US (total 87 subjects) in the TRILUMINATE trial (CE mark trial). Out of the 87 subjects, 85 had completed their 30-day follow-up. Mean age of the study population was  $77.8 \pm 7.9$  years, and a majority of the subjects were female (65.9%). All subjects had moderate or greater TR, with the majority (94.0%) having severe TR. A majority of the subjects had significant comorbidities including atrial fibrillation (91.8%), hypertension (85.9%), and renal disease (45.9%) being the most common. All subjects were symptomatic with NYHA  $\geq$ II, with a majority (74.7%) of the subjects being in NYHA III/IV. Subjects had diminished quality of life and functional capacity with a mean KCCQ score of  $52.19 \pm 21.85$  points and a mean 6-minute walk test (6MWT) distance of  $277.47 \pm 137.20$  m.

An average of  $2.2 \pm 0.8$  clips were implanted per procedure with at least 1 clip implanted in all subjects. Implant success and acute device success rates were each 100%, and the acute procedural success rate was 91.6%. Of the 185 clips implanted in 85 subjects, 77.3% were in the anterior-septal leaflet position, 20.0% in the septal-posterior position and 2.7% in the anterior-posterior position. Mean total procedure, device, and fluoroscopy durations were  $152.7 \pm 57.8$  min,  $75.2 \pm 43.1$  min and  $23.3 \pm 17.8$  min respectively.

Primary effectiveness endpoint of TR reduction of least 1 grade at 30-days was successfully met. At 30 days, 86.6% of subjects had their TR reduced by at least 1 grade, with a one-sided 97.5% lower confidence limit of 77.3%, which was significantly greater than the pre-specified performance goal of 35% ( $p < 0.0001$ ). At 30 days, a significantly greater proportion (79.8%) of subjects showed improvement in NYHA functional class and were categorized as NYHA class I or II compared to 25.3% of subjects at baseline. Subjects experienced a significant improvement in their quality of life assessed using the Kansas City Cardiomyopathy Questionnaire, with scores improving from  $52.19 \pm 21.85$  at baseline to  $67.24 \pm 22.24$  at 30 days, a mean improvement of  $14.20 \pm 16.74$  points. Similarly, subjects improved their 6MWT distance from  $277.47 \pm 137.20$  at baseline to  $304.46 \pm 109.74$  at 30 days, a mean improvement of  $47.5 \pm 69.7$ m.

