**Baseline assessments may occur on the day of treatment but prior to randomization (for randomized subjects):**

- Baseline TTE imaging must be obtained. If screening TTE imaging was performed within 14 days, then screening images may be used as baseline.
- A physical exam including an assessment of subject's cardiac status and vital signs measures must be completed.
- Blood tests performed.
- Concomitant cardiovascular medications must be documented.
- A 12-lead ECG must be performed.

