### 7.6.2 Pre-Procedure

#### 7.6.2.1 Pre-Procedure Anticoagulation/Antiplatelet Therapy

Perform pre-procedure anticoagulation/antiplatelet therapy according to institution standard of care for transcatheter cardiac procedures. Otherwise, perform anticoagulation/antiplatelet therapy according to the recommended therapy in this section.

Discontinue the use of warfarin for at least three (3) days prior to the scheduled TriClip™ procedure and it is suggested that the international normalized ratio (INR) is  $\leq 1.7$  prior to the TriClip™ procedure. Similarly, discontinue dabigatran or factor Xa inhibitors medications for a sufficient duration to ensure restoration of normal coagulation, or per institution standard of care. Subjects may be treated with heparin during this period at the treating physician's discretion. If heparin is used, it should be discontinued  $\geq 8$  hours prior to the TriClip™ procedure for subcutaneous low molecular weight heparin (LMWH) and  $\geq 4$  hours prior to the TriClip™ procedure for intravenous unfractionated heparin (UFH).

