#### 7.8.1.2 Antiplatelet/Anticoagulation Therapy

Following placement of the TriClip™ device, anticoagulation therapy is prescribed. If a loading dose of clopidogrel was not given prior to the TriClip™ procedure, it may be administered after the procedure at investigator discretion. Post- TriClip™ procedure anticoagulation is as follows:

1. Reinitiate warfarin, dabigatran or factor Xa inhibitor (if discontinued for the TriClip™ procedure) at pre-procedure levels or as appropriate. If chronic oral anticoagulation is used, aspirin and clopidogrel use are not recommended, but are allowed if otherwise indicated for other conditions.
2. If chronic oral anticoagulation is not used, it is strongly recommended that either daily clopidogrel (75 mg) and/or aspirin ( $\geq 75$  mg) is administered for 6 months or longer. If aspirin is to be used, a loading dose of 325 mg acetylsalicylic acid (ASA) may be administered either pre- or immediately post- TriClip™ procedure followed by  $\geq 75$  mg per day for 6 months or longer at the Investigator's discretion.

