## TRILUMINATE Pivotal CIP (Version F)

TriClip™ must also be evaluated for device integrity. Required tests and procedures outlined below must be completed. Timing of specific tests will follow the Clinical Evaluation Schedule (**Table 1**) outlined below. These clinical assessments are standard assessments for most cardiac/structural heart interventional procedures and therefore should be administered per standard of care at each Institution. All visits and tests must be completed even if the subject is in hospital. Refer to the Schedule of Events table section 7.15 for timing of below listed tests.

- 12-lead ECG
- Blood draw
- Physical exam including vital signs (weight, heart rate and blood pressure)
- Echocardiogram – TTE at all follow-up visits
- Modified Rankin Scale (Required at visits occurring after onset of stroke)
- 6-Minute Walk Test (6MWT)– See **APPENDIX XIII** for 6 Minute Walk Test Guidelines
- Concomitant cardiovascular medications assessment
- NYHA Functional Class assessment
- KCCQ QoL and SF-36 questionnaires to be completed by the subject – must be administered by “blinded” study personnel. Note: To minimize bias and undue influence, the QoL questionnaires will be completed by the subject, unless the subject is unable to complete the questionnaire on their own (a note to file must be completed to document the inability of subject to complete the questionnaire)
- Assess and record adverse events
- Assess and record protocol deviations

All subjects should continue to be monitored and treated per applicable standards of care consistent with the subject’s condition. The site Principal Investigator should collaborate with the other site investigators as applicable in determining the treatment strategy for all subjects enrolled at their site. The electronic case report forms will document changes in treatment strategy (i.e. new use of CRT, PCI, tricuspid valve surgery, and/or mitral valve surgery) and who was involved with determining changes in treatment strategy. Subjects implanted with the Clip must be evaluated for device integrity.

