**7.15 Schedule of Events**

**Table 1: Clinical Evaluation Schedule**

CIP Activity	Screening	Baseline	Procedure	Discharge (>16hr post-procedure)	30 days (-3/+14 days)	6 Month (±28 days)	12, 18 months, 2-5 years (±28 days)
Informed Consent Process	X						
Demographics	X						
Physical Examination & Vital Signs	X	X	X b	X	X	X	X
Local Heart Team Evaluation	X						
Cardiovascular History	X						
Medical History	X						
Cardiovascular Medications	X	X	X	X	X	X	X
Echocardiogram	X (TTE and TEE)	X (TTE only) a	X (TEE only)	X (TTE Only)	X (TTE only)	X (TTE Only)	X e (TTE only)
RHC	X						
CT c		X c			X c		X c (1 year only)
MRI		X c			X c		
CBC with differentials and platelet count	X	X a		X	X	X	X
Gamma-GGT d , BNP or NT-proBNP, CK or CK-MB, BUN, serum creatinine, AST, ALT, INR (while on anticoagulation), Bilirubin, Serum Sodium	X	X a		X	X	X	X
KCCQ		X			X g	X g	X e, g
SF-36		X			X g		X (1 and 2 year only) g
6-Minute Walk		X				X g	X e, g
NYHA FC	X	X		X	X g	X g	X g
12-lead ECG	X	X	X b	X	X	X	X
Modified Rankin Scale f				X	X	X	X
Hospitalizations	X (prior 12 months)	X	X	X	X	X	X
Adverse Events/Deviation		X	X	X	X	X	X
Device Deficiency			X	X	X	X	X
Withdrawal		X	X	X	X	X	X

a If performed within 14 days of assessment for screening, then screening can be used for baseline.

b Must be performed within 24 hours prior to procedure (Device, Single-arm and Roll-in Group).

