# TRILUMINATE Pivotal CIP (Version F)

c Only required for subjects in the imaging sub study.

d Only required for sites with capability.

e Not required at 18 months.

f Only required at visit after onset of stroke, if stroke occurred.

g These assessments during these visits should be completed by blinded personnel

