## MELD SCORE

The Model for End-Stage Liver Disease, or MELD, is a scoring system for assessing the severity of chronic liver disease. The following parameters are used to determine MELD score: Creatinine level, Bilirubin level, INR (international normalized ratio), and serum sodium level. The score is calculated as follows:

Candidates who are at least 12 years old receive an initial MELD(i) score equal to:

$0.957 \times \text{Loge}(\text{creatinine mg/dL}) + 0.378 \times \text{Loge}(\text{bilirubin mg/dL}) + 1.120 \times \text{Loge}(\text{INR}) + 0.643$   
Laboratory values less than 1.0 will be set to 1.0 when calculating a candidate's MELD score.

Study Document No: ABT-CIP-10249

Study Name: TRILUMINATE Pivotal

**CONFIDENTIAL:** May not be reproduced outside of Abbott without written permission from Document Control. This is a quality record which will be retained per the local retention policy.

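### MELD change is a listed endpoint for all subjects and needs INR, but Table 1 schedules INR only for subjects on anticoagulants

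*Protocol*

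**What the plan says.** The endpoint. Protocol sections 5.1.3 and 5.2.3 and SAP sections 1.4.1.3 and 1.4.2.3 list change in MELD from baseline to 30 days, 6 months, 12 months and then yearly to 60 months as the measure of liver function. None of the four restricts it by anticoagulant use.

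The formula. Protocol Appendix II, under MELD Score, states: "The following parameters are used to determine MELD score: Creatinine level, Bilirubin level, INR (international normalized ratio), and serum sodium level". The INR term is 1.120 × ln(INR). Laboratory values below 1.0 are raised to 1.0.

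The schedule. The chemistry row of Table 1 (Protocol 7.15) reads "serum creatinine, AST, ALT, INR (while on anticoagulation), Bilirubin, Serum Sodium". The condition attaches to INR alone. The footnotes do not widen it. Footnote d, "Only required for sites with capability", concerns gamma-GGT, and footnote a lets screening bloods from within 14 days stand as baseline. The visit text in section 7.10.2 lists a blood draw without naming assays and sends the reader back to the table: "Refer to the Schedule of Events table section 7.15 for timing of below listed tests". Section 7.3.1 likewise says only that blood tests are done at baseline.

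The subjects concerned. The note to exclusion criterion 18 keeps patients with a contraindication to anticoagulants alone eligible, and section 7.8.1.2 has a separate recommendation for subjects not on chronic oral anticoagulation. The protocol therefore expects such subjects.

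**The concern.** A site that follows Table 1 exactly will collect three of the four MELD inputs in a subject off anticoagulants. The change score needs INR at two time points, so a subject who is off treatment at either one has no scheduled pair. That includes subjects who start or stop treatment between the two.

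The MELD summary would then describe a subset selected by treatment, while the endpoint lists present it as an outcome of the whole cohort. A reader of a table headed simply as change in MELD would not know this unless the number without a paired INR were shown.

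**Working it through.** The plan gives no figure to reproduce here. The check has three parts: set the texts side by side, see whether the INR term matters, and gauge how many subjects are affected.

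**1. Is INR scheduled unconditionally anywhere?**

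| MELD input | Required by Appendix II | Scheduled in Table 1 |
|---|---|---|
| Creatinine | yes | all subjects |
| Bilirubin | yes | all subjects |
| Sodium | yes (second step) | all subjects |
| INR | yes | only while on anticoagulants |

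The only other readable mention of measuring INR is the suggested pre-procedure value in section 7.6.2.1. That is not a baseline or follow-up assessment and does not concern Control visits. The floor at 1.0 acts on a measured value and does not supply an absent one.

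**2. Can the INR term be ignored?**

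Initial score = 10 × [0.957 ln(creatinine) + 0.378 ln(bilirubin) + 1.120 ln(INR) + 0.643], with the bracket rounded to one decimal place. Take assumed values of creatinine 1.3, bilirubin 1.2 and sodium 137:

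- INR 1.0: 0.251 + 0.069 + 0 + 0.643 = 0.963, rounded to 1.0, score 10.
- INR 2.5: 0.963 + 1.120 × 0.916 = 1.989, rounded to 2.0, score 20.

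The term is too large to drop or to fill in by assumption.

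**3. How many subjects?**

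The documents do not give the share off anticoagulants. The nearest figure is in Protocol 2.1.4, on the earlier TriClip trial: "A majority of the subjects had significant comorbidities including atrial fibrillation (91.8%), hypertension (85.9%), and renal disease (45.9%) being the most common". Its complement, 100% − 91.8% = 8.2%, is a rough proxy, because atrial fibrillation and anticoagulant use are not the same thing. A range of 5% to 30% is assumed around it.

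| Group (N) | 5% | 8.2% | 30% |
|---|---|---|---|
| Randomized, all (450) | 22.5 | 36.9 | 135 |
| Randomized, primary analysis (350) | 17.5 | 28.7 | 105 |
| Single-arm (200) | 10 | 16.4 | 60 |

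Each entry is N × share at full enrollment, before deaths, withdrawals and missed visits.

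**4. Illustration only: INR moving with the drug**

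In a subject with INR at both visits, the unrounded shift before the sodium step is 10 × 1.120 × ln(INR2/INR1). An assumed on-drug change from 2.0 to 3.0 gives 11.2 × 0.405 = 4.5 points with no change in the liver; an unchanged INR gives 0. For initial scores above 11, the sodium step multiplies such a shift by 1 − 0.033 × (137 − Na), for example 0.77 at sodium 130. These values show what the formula can do. They do not estimate what will happen in this trial.

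**The case against.** The strongest reply is that little depends on this endpoint. It is descriptive, and gamma-GGT change is also a listed descriptive endpoint in both cohorts and needs no INR, although it is measured only where sites are able. Bilirubin, AST and ALT are scheduled for everyone. All of that stands and keeps the point minor.

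Second, a rule for absent INR may exist in the missing-data sections (Protocol 9.7, SAP 2.9), which are redacted, and sites may measure INR in routine care. Both are possible. Neither changes what Table 1 schedules, and routine-care values would not be collected uniformly.

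Third, a reader might infer that MELD change is distorted by peri-procedural warfarin handling, or differs between arms for that reason. Section 7.6.2.1 says "Discontinue the use of warfarin for at least three (3) days prior to the scheduled TriClip™ procedure", section 7.8.1.2 says "Reinitiate warfarin, dabigatran or factor Xa inhibitor (if discontinued for the TriClip™ procedure) at pre-procedure levels or as appropriate", and section 7.3.1 allows baseline tests on the day of treatment, so a low baseline INR followed by a higher one can be imagined. The documents do not support that as an expected effect:

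- Section 7.6.2.1 puts institutional standard of care first.
- Footnote a lets earlier screening bloods serve as baseline.
- In the Randomized cohort, baseline precedes randomization (4.2.1), and the Device procedure is scheduled after it (7.4).
- Section 7.10.1 asks that baseline medications stay unchanged unless clinically necessary. With stable treatment, much of any drug effect cancels in a change score.

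The sequence is easiest to picture in the Single-arm cohort, which has no randomization step. Even there it is only a possibility.

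**Conclusion.** The endpoint definition and the laboratory schedule do not agree. With the schedule as written, MELD change cannot be computed from protocol-scheduled data for a subject off anticoagulants at baseline or at the visit. This follows from the text alone.

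The size is uncertain. It is about 37 of 450 randomized subjects if the 8.2% proxy is accepted and about 22 to 135 over the assumed 5% to 30%, and nothing in the documents fixes the true share. No bias between arms is shown, and no test, power calculation or labeling claim is affected. It is a minor inconsistency, worth correcting because the correction is cheap.

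**What to change.** **Protocol.** Reconcile Table 1 with Appendix II by scheduling INR for all subjects at the visits where MELD is reported: baseline, 30 days, 6 and 12 months, and years 2 to 5. The existing condition can stay at screening, discharge and 18 months, except that where screening bloods stand in for baseline, INR must be run on that sample.

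**SAP 1.4.1.3 and 1.4.2.3.** Report MELD change in subjects with INR at both baseline and the visit, state how many lack the pair, and show bilirubin change alongside for all subjects. A split by anticoagulant status (on or off) is optional, because INR can move with the drug. Medications are already recorded at each visit, so it needs no new data. No change to anticoagulant treatment is proposed.

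**Cost.** One amendment with IRB/EC handling (Protocol 11.4 and 13.1), and one routine assay on an existing draw for subjects off anticoagulants. With 450 + 200 = 650 subjects and 8 MELD visits, before attrition and excluding roll-ins:

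- 650 × 0.05 × 8 = 260 assays over 5 years
- 650 × 0.082 × 8 = about 426
- 650 × 0.30 × 8 = 1,560

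Deleting the condition from the whole row would cost more, because the row also covers screening, discharge and 18 months. That is 650 × 10 draws plus about 425 discharge draws (225 Device + 200 Single-arm) = 6,925, or about 346 assays at 5% and 2,078 at 30%.

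INR not measured at past visits cannot be recovered; for those visits only the SAP reporting helps.

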# TRILUMINATE Pivotal CIP (Version F)

c Only required for subjects in the imaging sub study.

d Only required for sites with capability.

e Not required at 18 months.

f Only required at visit after onset of stroke, if stroke occurred.

g These assessments during these visits should be completed by blinded personnel

## 8 ADVERSE EVENTS

To comply with worldwide standards and guidelines on clinical investigation adverse event reporting, the Sponsor has adopted uniform and worldwide applicable standard definitions and reporting timelines to be used and adhered to by the investigators.

### 8.1 Definition

#### 8.1.1 Adverse Event

An adverse event (AE) is any untoward medical occurrence, unintended disease or injury, or untoward clinical signs (including abnormal laboratory findings) in subjects, users or other persons, whether or not related to the medical device under investigation.

As part of ISO 14155 Section 3.2, the Adverse Event definition has the following notes:

Note 1: This definition includes events related to the medical device under investigation or the comparator.

Note 2: This definition includes events related to the procedures involved.

Note 3: For users or other persons, this definition is restricted to events related to medical devices under investigation.

#### 8.1.2 Serious Adverse Event

If the AE meets any of the criteria below, it is regarded as a serious adverse event (SAE).

- a) Led to a death,
- b) Led to a serious deterioration in health of the subject, that either resulted in:
  - 1. a life-threatening illness or injury, or
  - 2. a permanent impairment of a body structure or a body function, or
  - 3. in-patient hospitalization or prolongation of existing hospitalization, or
  - 4. medical or surgical intervention to prevent life threatening illness or injury or permanent impairment to a body structure or a body function or
  - 5. chronic disease
- c) fetal distress, fetal death or a congenital abnormality or birth defect.

**Note:** A planned hospitalization for a pre-existing condition, or a procedure required by the CIP, without a serious deterioration in health, is not considered to be an SAE.

### 8.2 Device Relationship

Determination of whether there is a reasonable possibility that an investigational product or device under investigation caused or contributed to an AE is to be **determined by the Investigator** and recorded on the appropriate CRF form. Determination should be based on

Study Document No: ABT-CIP-10249

Study Name: TRILUMINATE Pivotal

**CONFIDENTIAL:** May not be reproduced outside of Abbott without written permission from Document Control. This is a quality record which will be retained per the local retention policy.

**TRILUMINATE Pivotal CIP**  
(Version F)

assessment of temporal relationships, evidence of alternative etiology, medical/biologic plausibility, and patient condition (pre-existing condition).

### **8.2.1 Unanticipated (Serious) Adverse Device Effect [U(S)ADE]**

U(S)ADE refers to any serious adverse effect on health or safety or any life-threatening problem or death caused by, or associated with, a device, if that effect, problem, or death was not previously identified in nature, severity, or degree of incidence in the investigational plan or application (including a supplementary plan or application), or any other unanticipated serious problem associated with a device that relates to the rights, safety, or welfare of subjects.

### **8.2.2 Device Deficiency/Device Malfunction**

Device deficiency is defined as an inadequacy in the identity, quality, durability, reliability, usability, safety of performance of an investigational device including malfunction, use errors, or inadequacy in the information supplied by the manufacturer including labeling. This includes the failure of the device to meet its performance specifications or otherwise perform as intended.

Note 1: The definition includes device deficiencies related to investigational medical device or the comparator.

Note 2: Cyber-security incidents related to the investigational product, shall be reported as device deficiencies

A device malfunction is the failure of an investigational medical device to perform in accordance with its intended purpose when used in accordance with the instructions for use or CIP, or IB.

## **8.3 Adverse Event and Device Deficiency/Device Malfunction Reporting**

### **8.3.1 Adverse Event Reporting**

Safety surveillance and reporting starts as soon as the patient is enrolled in the clinical investigation. Safety surveillance and reporting will continue until the last follow-up visit has been performed, the subject is deceased, the subject concludes participation in the clinical investigation, or the subject withdraws from the clinical investigation. All adverse event data, including deaths and device deficiency data, will be collected throughout the time period defined above and will be reported to the Sponsor on an eCRF within an Electronic Data Capture (EDC) database. Additional information, with regard to an adverse event, should be updated on the appropriate eCRF within the EDC.

Unchanged, chronic, non-worsening or pre-existing conditions are not AEs and should not be reported.

Non-cardiac related abnormal laboratory values will not be considered AEs unless:

- 1) the investigator determined that the value is clinically significant,
- 2) the abnormal lab value required intervention, or
- 3) the abnormal lab value required subject termination from the study.

An offline form will be made available to allow the investigator to report SAEs in the event the entry cannot be made in the EDC. This does not replace the EDC reporting system. All information must still be entered into the EDC system as soon as feasible.

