**Screening assessments within 90 days prior to Eligibility Committee Review:**

- Transthoracic and transesophageal echocardiographic (TTE and TEE) images to be obtained and submitted to the ECL. Site must review the TEE images and confirm that subject has TR and suitable tricuspid valve anatomy, without intracardiac mass, thrombus or vegetation. Abbott personnel may provide support to sites in reviewing TEE images. See Appendix X and XI for echo protocol.
  - If the TEE is not standard of care at the site, the subject must provide informed consent prior to the echocardiographic study.
- Medical history must be obtained, including review of subject's medical records.
- Physical exam including vital signs (weight, heart rate and blood pressure)
- Blood test performed.
- Right heart catheterization to assess and rule out pulmonary hypertension as the cause of TR.
- Subject is examined by the site investigator experienced in treating heart failure, to assess the subject for appropriateness and optimization of medical and device therapy.
- Subject is evaluated by the site local heart team to confirm that they are adequately treated per applicable standards, including for coronary artery disease, left ventricular dysfunction, mitral regurgitation, TR and heart failure. Subjects with current or prior symptoms of heart failure and reduced LVEF must be on stable GDMT recommended according to current guidelines as standard of care for heart failure therapy in the United States. See '**APPENDIX II: Definitions**' for definition of optimal therapy.
- NYHA Functional Class assessment.
- A 12-lead ECG must be performed.
- Subject's pertinent medical information will be assessed by the EC. After the ECL has confirmed subject eligibility, sites will be notified by Sponsor to compile and submit information to assess clippability to the EC.

The following screening information must be captured on the appropriate electronic Case Report Forms (eCRFs):

- Inclusion and Exclusion criteria
- Demographics (e.g., age at time of consent, gender, race/ethnicity)
- Informed Consent date

In case the subject does not meet all inclusion criteria or meets any of the exclusion criteria, the subject is considered a screening failure. The Principal Investigator or the delegated clinical investigation personnel will record the screening failure in the hospital records and on a screening log as required.

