## **6.4 Subject Enrollment**

A patient is considered enrolled in the clinical investigation from the moment the patient provides written informed consent and has been confirmed to meet all inclusion criteria and none of the exclusion criteria. .

Subjects will be assigned a subject ID upon informed consent and entry into the database. Such subjects are registered in the trial.

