## **16.4 Risks Associated with Participation in this Clinical Investigation**

Protocol required assessments are summarized in Section 7.15, Table 1, Clinical Visits and Schedule of Assessments. Most of these clinical assessments are standard for most cardiac/structural heart interventional procedures and are administered per the standard of care at each institution, and do not constitute an additional risk for the clinical investigation participants.

Study specific assessments that may not be considered standard of care include protocol required transesophageal echocardiography (TEE) assessments performed at screening, baseline and during protocol defined follow up visits. TEE is a commonly used safe technique in cardiac interventions that requires conscious sedation or general anesthesia, depending on hospital standard practice. In the exceptional occasion if complications arise during the TEE procedure, it may be necessary to convert to an open surgical procedure. Emergency surgical back-up should be available as per the institution's standard procedures.

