3.2 Adverse Events

All adverse device effects, serious adverse device effects, UADEs, and USADEs will be summarized for all enrolled subjects in terms of the number of events, the percentage of subjects with events per MedDRA coding. Procedure related AEs may also be summarized.

Statistical Analysis Plan

All CEC adjudicated adverse events will be summarized for all subjects who enrolled in the trial by treatment group in terms of the number of events, and the percentage of subjects with events. Moreover, COVID-19 related AEs will be summarized in terms of number of events, the percentage of subjects with events per AE term.

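### Safety reporting starts at enrollment, so the visible plan does not require reporting of harms from screening procedures done after consent

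*Protocol*

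**What the plan says.** Protocol 8.3.1 fixes the start of reporting: "Safety surveillance and reporting starts as soon as the patient is enrolled in the clinical investigation". It then ties collection to the same period: "All adverse event data, including deaths and device deficiency data, will be collected throughout the time period defined above".

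Section 6.4 counts a patient as enrolled once he or she "provides written informed consent and has been confirmed to meet all inclusion criteria and none of the exclusion criteria". Someone who has only consented has a different status: "Subjects will be assigned a subject ID upon informed consent and entry into the database. Such subjects are registered in the trial".

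Section 6.2.1 gives the list headed "Screening assessments within 90 days prior to Eligibility Committee Review". It includes TTE and TEE images for the echocardiography core laboratory (ECL) and this item: "Right heart catheterization to assess and rule out pulmonary hypertension as the cause of TR". The screening items that the section names for the eCRF are the eligibility criteria, demographics and consent date.

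Section 16.4 says that the TEE required at screening may fall outside standard of care and involves sedation or general anesthesia. It adds: "In the exceptional occasion if complications arise during the TEE procedure, it may be necessary to convert to an open surgical procedure".

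SAP 3.2 says that device effects "will be summarized for all enrolled subjects in terms of the number of events". Its summary of events adjudicated by the Clinical Events Committee is likewise confined to subjects who enrolled.

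**The concern.** The protocol asks consented patients to undergo invasive tests and describes one of them as a risk of taking part. It then starts the safety clock after those tests are over. If a patient is harmed by a screening TEE done for the trial, nothing in the visible text obliges the site to report it as an adverse event.

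The gap is also selective. A patient who recovers and passes screening at least reaches the Baseline visit. A patient whose complication makes them ineligible is a screen failure and stays outside adverse event reporting altogether, so the more serious the harm, the less likely it is to be seen.

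What is at stake is the account of the risk of participation. Section 11.9.3 asks the Data Monitoring Committee to protect patients not yet enrolled as well as those enrolled, and these are events it is not assured of receiving.

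**Working it through.** There is no stated figure to reproduce. The check sets the sections side by side in time order.

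1. **Consent.** Section 6.2.1 requires signed consent before any test that is not standard of care. Under 6.4 the patient is then registered, not enrolled.
2. **Screening tests.** TEE and RHC are required within 90 days before Eligibility Committee review (6.2.1).
3. **Can enrollment come before the tests?** No. Exclusion 1 is judged by RHC. Exclusion 9 concerns whether the valve can be evaluated by TTE and TEE. Exclusion 21 concerns intracardiac mass, thrombus or vegetation, which 6.2.1 has the site look for on the TEE. Whether confirmation means the site's or the committee's, both tests come first.
4. **Enrollment.** Safety reporting opens here (8.3.1).
5. **Baseline.** This visit falls within 14 days after the committee confirms eligibility (7.3.1). In Table 1 the Adverse Events row is blank at Screening and has its first mark at Baseline. The table agrees with 8.3.1, so the late start is the stated rule and not a slip in one sentence.

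**Length of the gap for a patient who goes on to enroll**, assuming committee review and confirmation fall on the same day:
- earliest screening test to start of reporting: up to about 90 days;
- earliest screening test to first scheduled adverse event assessment: 90 + 14 = about 104 days.

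**For a screen failure**, the reporting period never opens.

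Two other provisions do not change this. Section 8.1.1 includes procedure-related events in the definition of an adverse event, but that says what counts, not when collection begins. The extra TEE within 3 days before the procedure (7.6.2.4) comes after enrollment and is already covered.

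**Number of events.** This would be (post-consent screening tests done for the trial) × (complication rate). The documents give neither factor.

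**The case against.** The best reply is that 8.3.1, 6.4 and Table 1 agree with one another, so this is a choice about coverage and not a contradiction, and that other provisions may catch these events.

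- **Section 12.4** collects CRF data from everyone who consents, including those who fail screening. It names no adverse events, and the specific screening list in 6.2.1 has none. If it was meant to cover them, it conflicts with 8.3.1 and Table 1.
- **The SAE timeline** speaks of all SAEs without repeating the enrollment limit. It sits inside 8.3.1, whose period begins at enrollment.
- **The Hospitalizations row of Table 1** is marked at Screening (for the prior 12 months) and at Baseline, and 7.3.1 has the site reassess eligibility at Baseline. For a patient who enrolls, an admission after a screening test could therefore be recorded, but not with an adverse event or relatedness assessment.
- **Material not visible here**, such as the case report forms, the monitoring plan and the study-specific Safety Plan mentioned in Appendix XV, might require more. The conclusion is therefore limited to what the visible plan requires.
- **Not every test is caused by the trial.** Section 6.2.1 accepts standard-of-care tests done before consent, and 16.4 says most assessments are standard. Only TEE is named as possibly study-specific; RHC is required but is never described as done solely for the trial. This stands and narrows the point.
- **The open-surgery sentence in 16.4** closely resembles the index-procedure wording in 7.6, and 16.4 refers to follow-up TEEs that Table 1 does not schedule. It may be carried-over text. It shows that the plan acknowledges a TEE risk, not how large that risk is.
- **The quoted phrase in SAP 3.2** concerns device effects, which a screening harm would not be in any case. The restriction of the adjudicated-event summary to enrolled subjects is the more relevant support.

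**Conclusion.** The gap is real and limited. The visible plan does not require reporting of adverse events between consent and enrollment. Harms from required screening procedures done after consent (TEE where it is not standard of care, and RHC where it is not routine) fall into that interval. A patient made ineligible by such a harm is never brought into reporting.

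Three stronger conclusions are tempting but unsupported:

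- **That these harms will be counted as zero, or that nobody will see them.** The text shows only that reporting is not required. Sites may report under local rules, and part of the relevant documentation is not visible.
- **That every screening TEE and RHC is done only because of the trial.** The protocol accepts earlier standard-of-care results.
- **That a number of missed events can be estimated** by applying a complication rate to the 450 + 200 = 650 planned randomized and Single-arm subjects. No rate is given. The 650 includes patients whose tests were routine care and leaves out the screen failures who are the main worry.

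No hypothesis, endpoint, power figure or success rule is touched; the MAE endpoint counts events after femoral vein puncture. The conclusion rests on reading the explicit start date in 8.3.1 as governing the general CRF statement in 12.4. The change is a worthwhile, inexpensive improvement to patient safety reporting.

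**What to change.** - **Protocol 8.3.1:** start reporting of SAEs, and of adverse events related to protocol-required screening procedures, at signed consent. Include screen failures and follow them until the event resolves.
- **Table 1:** add a mark under Screening in the Adverse Events row, so that the schedule agrees with 8.3.1 and with the CRF statement in 12.4.
- **SAP 3.2:** add a separate listing of screening-period events in all consented subjects, since the present summaries are built on enrolled subjects.
- **Leave unchanged:** the definition of enrollment and the MAE and effectiveness clocks.

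The cost is a short text change, one table cell, one listing and some extra reporting by sites on patients who fail screening. Nothing in the endpoints, alpha or power changes.
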